Table 2 Outcome measure comparisons and rationale

Test condition	Comparison	Rationale
Sentences in noise S0Nrearhalf babble (65 dB SPL) Sentences in noise S0N3 babble (65	Treatment: Nucleus 8 SCAN+FF Control: Nucleus 8 SCAN Treatment: Nucleus 8 SCAN+FF	ForwardFocus is designed to reduce sounds that originate from behind the listener. The inclusion of S0Nrearhalf and S0N3 speaker configurations, with the noise originating from behind, will facilitate confirmatory testing of SCAN+FF compared with the default SCAN configuration while controlling for the sound processor hardware including new microphones, and the new underlying scene classifier.
dB SPL)	Control: Nucleus 8 SCAN	This will be the first evaluation of SCAN+FF using a more disparate and variable noise type (S0Nrearhalf) and fixed-speaker noise (S0N3), and will provide an indication of the performance of ForwardFocus Auto in a variety of noise positions.
CNC words in Quiet (50 dB SPL)	Treatment: Nucleus 8 standard directionality Control: Nucleus 7 standard directionality	
SSQ12	Treatment: Nucleus 8 Sound Processor Control: Nucleus 7 Sound Processor	The SSQ includes a variety of hearing situations that reflect the reality hearing in the everyday world. The inclusion of this measure, coupled alongside the inbooth testing, allows for a complete picture of benefit associated with the signal processing technology. Study subjects will be asked to complete the SSQ12 at two time points in the study; 1) at study entry, where scores will reflect their experience with their own sound processor, 2) after take home use with the Nucleus 8 Sound Processor.

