6.2 Secondary Objective

- To evaluate adult cochlear implant speech perception in spatially separated speech and noise (S0N3) with the CP1110 Sound Processor with ForwardFocus ON (SCAN) compared with ForwardFocus OFF (SCAN)
- To evaluate adult cochlear implant speech perception in quiet with the CP1110 Sound Processor and the Nucleus 7 Sound Processor
- To evaluate adult cochlear implant subjective hearing performance and sound quality with the CP1110 Sound Processor and Nucleus 7 Sound Processor
- To evaluate acceptance and satisfaction of the CP1110 Sound Processor

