Table 4. Take home conditions for non-SCAN users

	SNR-NR	Directionality	ForwardFocus
P1 Nucleus 8 Custom	*	User preference (Standard, Zoom, BEAM)	Manual
P2 Nucleus 8 SCAN+	✓.	SCAN	Automatic

At the end of the study visit, the Investigator will set up all devices required for the subject's takehome use. This may include pairing to their own or loaner assistive listening devices, fitting any retention accessories, installing the compatible Nucleus Smart App on subject's own or a loaner smartphone, and pairing the investigational processors to the phone accordingly.

Visit 2

Included in this period:

- Take-home feedback
- Device optimisation including the issuance of new firmware and new features as made available throughout the course of the trial (if required)
- Usability Questionnaire/interview
- Nucleus 8 Questionnaire 1 SSQ12 – Nucleus 8
- Adverse Events and Device Deficiencies

Take-home feedback

After the take home period, study subjects will be asked about their experience with the Nucleus 8 Sound Processor. The study investigator will optimize the devices if required. Device deficiencies and adverse events experienced during this take home period will be recorded if not already.

Questionnaires

Based on their experience with the Nucleus 8 SP, study subjects will be asked to complete the SSQ12 Questionnaire, usability interview and the Nucleus 8 Questionnaire 1.

Additional usability questions or interviews may be completed during this visit.

CIP Number: CLTD5810

Take-home use

At the end of the study visit the Nucleus 8 SP programs will be re-programmed onto the study devices. See instructions under visit 1 'Take-home use' for programs to be used and instructions.

Visit 3

Included in this period:

- Take-home feedback
- Device optimisation including the issuance of new firmware and new features as made available throughout the course of the trial (if required)
- Adverse Events and Device Deficiencies

Take-home feedback

After the take home period, study subjects will be asked about their experience with the Nucleus 8 Sound Processor. The study investigator will optimize the devices if required. Device deficiencies and adverse events experienced during this take home period will be recorded if not already.

Take-home use

At the end of the study visit the Nucleus 8 SP programs will be re-programmed onto the study devices. See instructions under visit 1 'Take-home use' for programs to be used and instructions.

Visit 4

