Included in this period:

- Take-home feedback
- Device optimisation including the issuance of new firmware and new features as made available throughout the course of the trial (if required)
- Nucleus 8 Questionnaire 2
- Adverse Events and Device Deficiencies

Take-home feedback

After the take home period, study subjects will be asked about their experience with the Nucleus 8 SP. The study investigator will optimize the devices if required. Device deficiencies and adverse events experienced during this take home period will be recorded if not already.

Questionnaires

Based on their experience with the Nucleus 8 SP, study subjects will be asked to complete the Nucleus 8 Questionnaire 2.

Take-home use

At the end of the study visit the Nucleus 8 SP programs will be re-programmed onto the study devices. See instructions under visit 1 'Take-home use' for programs to be used and instructions.

Additional Visits

During this period of take-home use, between visits 4 and the completion visits. Subjects may come into the clinic or a remote session will be scheduled for device optimisation and troubleshooting, or to receive new features available during development of the product. This visit may include the following:

- Take-home feedback
- Device optimisation including the issuance of new firmware and new features as made available throughout the course of the trial (if required)
- Adverse Events and Device Deficiencies
- Speech Perception Tests (in-clinic only)
 - o Sentences in noise
 - S0Nrearhalf
 - S0N3

Words in quiet (CNC)

Sentence in noise test

See section 7.3.7 for the procedural provisions relating to speech perception testing that will introduced if Covid restrictions are in place during this study period.

Table 5. Speech in Noise test conditions (S0Nrearhalf and S0N3). Whisper, WNR, ADRO and ASC will be activated according to user preference.

	SNR-NR	Directionality	ForwardFocus
Nucleus 8 FF 'Auto'	1	SCAN	✓
Nucleus 8 SCAN	¥	SCAN	

In booth speech perception testing will be conducted using the signal processing combinations and hardware listed in Table 5. The order of testing will be conducted according to the counterbalancing outlined in Section 7.2.7.

For S0Nrearhalf and S0N3 speech in noise tests, all subjects will be tested in the unilateral condition and each subject will have their contralateral ear (non-test ear) blocked with an ear plug for all test conditions.

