- Signal from in front (0 degrees)
- 2 lists of 50 words each

At the end of each run, the investigator will record the result on the worksheet and in the EDC.

Visit 5 – Completion

- Take-home feedback
- Adverse Events and Device Deficiencies
- Return devices

Take-home feedback

After the take home period, study subjects will be asked about their experience with the Nucleus 8 Sound Processor. The study investigator will optimize the devices if required. Device deficiencies and adverse events experienced during this take home period will be recorded if not already.

Return devices and study completion

At the end of the study, subjects will return to their own device with the commercially available firmware.

Adaptive procedure:

While there are no expected unplanned product changes, early product can be sensitive to the low-risk issues identified in Table 7. During this study these product issues may be identified by study subjects during the in-clinic testing sessions that require optimisation or correction, and an adaptive procedure allows for product feedback to be collected from study subjects, for the product to be updated, and for the updated product to be reissued to study subjects for continued testing. Table 7 identifies how issues will be investigated and retested by the research subjects.

Before initiating speech perception testing, study investigators may ask study subjects to use the investigational medical device in settings at Cochlear Limited or on Campus at Macquarie University.

New Device Iteration:

If a product issue is identified either prior to or during the speech perception evaluation that may have an impact on speech perception outcomes, the formal testing will be paused for subjects while the change is made and a new version of the Sound Processor system will be developed and issued to study participants.

If the product issue was present for all subjects, then all subjects will be asked to repeat any testing that had occurred.

Table 7. Product adaptation categories and product issue examples

Category	Example of a product issue	Action
Sound quality	Study subjects may provide feedback on the general sound quality of the Sound Processor in everyday sound environments like noisy cafes, quiet rooms or windy situations.	If the issue has an impact on performance the product will be updated and speech perception will be re-evaluated by subjects.

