	Study subjects may provide feedback that the Sound Processor is unacceptably noisy or has an unacceptably noticeable buzzing.	If the issue has an impact on performance the product will be updated and speech perception will be re-evaluated by subjects.
Intermittency	Study subjects may provide feedback that the Sound Processor is not outputting a consistent signal with gaps in stimulation.	If the issue has an impact on performance the product will be updated and speech perception will be re-evaluated by subjects.
General bugs and product issues:	While all measures have been undertaken to test each of the features with the Nucleus 8 (CP1110) Sound Processor, there may be unforeseen issues that are exposed through usage in the environments used in the study.	General issues will be judged on a case by case basis. If it is judged that the issue has an unacceptable impact on performance, the product will be updated and re-evaluated by subjects.

All product issues will be recorded as device deficiencies. The Sound Processor will be considered mature for speech perception testing when all product optimisations that impact on performance have been made.

Multiplicity and Type I error

This adaptive procedure will only be incorporated when subjective issues are raised by study subjects, and will not be based on the speech perception scores collected during the session.

No repetition of speech perception will occur after the database has been locked. As such, no control of Type I error is necessary when sound quality or intermittencies are identified during data collection.

Visit 0	Visit 1	Visit 2	Visit 3	Visit 4	Additional Visit(s)	Visit 5
•Screen •Consent •Demographics •Eligibility •Medical History •Hearing History •Device History	•SP Fitting •Usability Interview •Baseline Questionnaire •Sound Quality •Usability •SSQ12 Nucleus 7	•Take-home feedback •SP Optimisation (as required) •Nucleus 8 Questionnaire 1 •SSQ12 Nucleus 8	•Take-home feedback •SP Optimisation (as required)	•Take-home feedback •Nucleus 8 Questionnaire 2 •Start extended take-home use	•Take-home feedback •SP Fitting Optimisation (as required) •Troubleshooting •SONrearhalf •SON3 •CNC Words	 Take-home feedback Study completion (all devices returned and subjects reverted to own SP)

Figure 4. Overview of planned visits

Periods of take-home use

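### Does the repeat-testing rule after a device update leave it open which SSQ12 rating is tested, and with what Type I error?

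*Combined protocol and SAP*

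**What the plan says.** The adaptive procedure in Section 7.3.6 pauses formal testing if a product issue that could affect speech perception outcomes is found before or during the speech evaluation. A new version is then issued, and "If the product issue was present for all subjects, then all subjects will be asked to repeat any testing that had occurred". Readiness is defined for speech tests: "The Sound Processor will be considered mature for speech perception testing when all product optimisations that impact on performance have been made". On multiplicity the section says "This adaptive procedure will only be incorporated when subjective issues are raised by study subjects, and will not be based on the speech perception scores", adds that speech perception is not repeated after database lock, and concludes: "As such, no control of Type I error is necessary when sound quality or intermittencies are identified during data collection".

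The SSQ12 is a secondary endpoint serving the objective "To evaluate adult cochlear implant subjective hearing performance and sound quality with the CP1110 Sound Processor and Nucleus 7 Sound Processor". Sections 9.3 and 9.7 test it for non-inferiority with margin -1 at one-sided 0.025. The Nucleus 7 rating is taken at Visit 1. At Visit 2, "study subjects will be asked to complete the SSQ12 Questionnaire, usability interview and the Nucleus 8 Questionnaire 1". Table 2 says of the SSQ12: "The inclusion of this measure, coupled alongside the inbooth testing, allows for a complete picture of benefit associated with the signal processing technology". New firmware may be issued from Visit 2 onwards. Additional visits after Visit 4 may be used for troubleshooting "or to receive new features available during development of the product", and the Schedule of Events places the booth tests at those visits.

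**The concern.** The repeat rule does not define testing. If it excludes the SSQ12, that result stays attached to whatever version subjects wore up to Visit 2, while booth tests may be run later on an updated version. Table 2 presents the two as a joint picture of benefit.

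If it includes the SSQ12, a second Nucleus 8 rating exists and the plan does not say which one is tested. The Type I paragraph would not help. A trigger based on subjects' complaints may be unrelated to speech scores, but it is hardly unrelated to a questionnaire about subjective hearing and sound quality. The SSQ12 is one of only two formal comparisons of Nucleus 8 with Nucleus 7 (CNC words is the other), so a free choice between ratings would matter.

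**Working it through.** **The plan's own figure.** Section 9.4 gives 17 subjects, for the SRT test. A paired t-test with margin 1 dB, SD 1.36 dB, true difference 0 and one-sided alpha 0.025 has power 0.785 at n = 16 and 0.812 at n = 17, so 17 reproduces. There is no corresponding figure for the SSQ12 or the adaptive procedure, so the question turns mainly on the text.

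**Which rating is tested?**

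- Section 9.2: one SSQ12 questionnaire per processor condition per person.
- Section 7.3.3 and Table 2: two SSQ12 time points, study entry (own processor) and after take-home use of Nucleus 8.
- Schedule of Events, the Visit 2 text in 7.3.6 and Figure 4: Nucleus 8 SSQ12 at Visit 2 and nowhere else.

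These agree. The paired difference is Visit 2 minus Visit 1.

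**What does the repeat rule cover?**

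- The condition for a new iteration is an issue that may affect speech outcomes.
- Three of the four Table 7 actions name re-evaluation of speech perception. The fourth, for general bugs, names no measure.
- The maturity rule and the database-lock sentence name speech perception only.
- Section 7.3.3 classes the SSQ12 as a subjective rating, apart from the speech tests in 7.3.1 and 7.3.2.

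The natural reading is that booth tests are repeated. The Type I paragraph is confined to speech scores because those are what gets repeated.

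**What if the SSQ12 were repeated anyway?** All figures below are at a true difference of -1.

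1. One rating fixed in advance: 0.025 (simulated 0.0245 to 0.0253).
2. Either of two whole-cohort ratings may count: at most 2 × 0.025 = 0.05. With independent ratings, 1 - 0.975² = 0.0494.
3. Independence is implausible because both differences subtract the same Visit 1 score. With equal variances σ² and a common correlation r among the three ratings, each difference has variance 2σ²(1 - r) and their covariance is σ²(r - r - r + 1) = σ²(1 - r), so they correlate (1 - r)/[2(1 - r)] = 0.5. At n = 20 the simulated error is 0.046 at correlation 0.5 and 0.040 at 0.8.
4. Complaints alone trigger replacement (assumed 25% or 50% chance of an update): the highest values are 0.030 at correlation 0.5 and 0.026 at 0.8 for n = 20, and 0.029 and 0.027 for n = 17.
5. Only the lowest raters re-rate and are replaced (assumed 2 to 10 of 20): 0.033 to 0.038 at correlation 0.9, rising to 0.074 to 0.137 at 0.5. The 0.05 ceiling in step 2 therefore holds only if the whole cohort is re-rated.

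Steps 2 to 5 each need a rule for choosing or replacing ratings that appears nowhere in the plan. The correlations, trigger rates and numbers re-rating are assumptions too. Steps 2 to 4 also put both ratings at the same true mean, although a repeat would follow a product change. These figures describe a different plan from the one written.

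**Version mismatch.** The documents give no update probability and no effect of an update on SSQ12, so no size can be computed. It is zero if nothing is issued after Visit 2, and Section 7.3.6 says unplanned changes are not expected.

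**The case for a change.** The strongest case is that the plan never states this reading. The general-bugs action says only that subjects re-evaluate the product. Section 7.3.7 speaks of testing at home, and Section 9.10 lists questionnaires under its tests and comparisons, so the word is not reserved for the booth. Firmware can change at Visits 2, 3, 4 and later. Delivery of new features falls outside the repeat rule altogether. Investigators are unblinded sponsor employees. A sentence naming the Visit 2 rating would cost almost nothing.

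Part of this stands. The wording is loose, and an update after Visit 2 could separate the SSQ12 version from the booth version. An update during the recruitment period of about two months could also mix versions among the Visit 2 ratings.

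The rest is weaker. The list in 9.10 does not include the SSQ12, and the home-testing phrase sits in a paragraph on remote device programming. Subjects complete the SSQ12 themselves on paper, which limits investigators' influence on the answers. It would not prevent a choice between two ratings, but only one Nucleus 8 rating is scheduled. The mismatch is also less sharp than it looks. Both noise tests compare Nucleus 8 with itself, and the CNC test uses standard directionality, so the booth tests already address different contrasts from the SSQ12. Table 2 presents complementary measures and does not promise identical firmware.

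**Conclusion.** No change follows. This is missing detail that an analyst following the plan would fill correctly: the Visit 2 rating is the tested Nucleus 8 score, there is one test, and its one-sided error is 0.025. That assumes the schedule is followed and that any extra SSQ12 collected after an update is treated as supplementary. Fixing the tested rating in writing would restate what Section 9.2, Section 7.3.3 and the Schedule of Events already imply.

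The possible version difference between SSQ12 and booth results is a fair trade-off of rating subjective benefit early in a study that allows product updates. Its size and direction are unknown, and it does not touch the primary endpoint. It can be described in the report from records already planned: software supply is tracked (Section 12), product issues are logged as device deficiencies (7.3.6), and device exposure is collected at Visits 1 to 5 and at additional visits (Schedule of Events).

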7.3.7 Procedural mitigation relating to COVID-19

Due to the physical distancing restrictions in place during the COVID-19 pandemic, optional device programming and procedural provisions may be introduced. These measures are to support the continuation of this project, while ensuring the safety of subjects and study staff.

- Screening and consent: See section 10 for the consent process. If COVID-19 restrictions also
 restrict research candidates from attending the study site, screening and consent may be
 performed via phone call or video conference. Paper copies of the consent form will be
 provided via mail/courier and subjects will be asked to use a prepaid envelope to return one
 original signed copy to the site.
- Device programming: Subjects may be asked to commence take-home testing through remote management. Devices, accessories, questionnaires, and instructions may be sent to subjects via courier, so that they do not need to attend the clinic. Prior to shipping, each subject's Nucleus 8 study sound processor(s) will be connected to the fitting software, Custom Sound Pro. The subject's MAP(s) from their own processor(s) are saved in their individual Custom Sound Pro file. This will be converted to their Nucleus 8 sound processor MAP(s), and their preferred programs written to the study processor. If a subject's most recent MAP(s) are not retrievable either from the site's database or the subject's clinical audiologist, remote management will not be possible until they are able to attend the site to have their own processor(s) connected to the software. For subjects who do not wish to participate in remote study and device management, the device programming and fitting will be performed in clinic once restrictions in New South Wales are eased.
- Usability interviews: Usability assessments may be conducted remotely to accommodate situations where test participants are unable to, or would prefer not to, travel to a site in order to perform testing. In the remote scenario, the usability interview will be conducted via video conferencing software. Subjects will be provided with all devices, accessories and user manuals required for the testing.
- Speech perception: Speech perception testing can only be conducted at the study sites. If
 restrictions are ongoing at the planned time of these study visits, these tests may be moved to
 later in the study. As such, speech perception tests have been decoupled from specific visits.
 If time permits, and study subjects are willing, all speech perception tests may be conducted
 on the same day. All comparisons for a specific endpoint test will be completed on the same
 day.

7.4 Safety Evaluations and Procedures

The risks and anticipated ADEs for the Nucleus 8 SP, as identified in Sections 8.2 and 8.3 of the CIP, will be assessed in the clinical investigation via reporting of all AEs/ADEs from the time of first subject first visit until last subject last visit.

Safety data adjudication may be conducted by the Sponsor's Medical Officer in accordance with the Sponsor's standard operating procedures.

7.4.1 Concomitant Medication and Therapies

All concomitant medical treatments will be collected as part of this study.

7.5 Equipment Used for Evaluation of Performance and Safety

7.5.1 Software

Speech testing in quiet and noise will be performed via the adaptive Australian Sentence Test in Noise (AuSTIN) test software (Dawson et al., 2013)

Devices and signal processing configurations will be programmed using Custom Sound 7.0.

7.5.2 Speech Perception

Speech perception performance in quiet will be assessed using a loudspeaker configuration with the speech from the front (S0).

Speech perception performance in noise will be assessed using a loudspeaker configuration with the speech from the front and noise from four roving locations in the rear hemisphere (S0Nrearhalf) and with speech from in front and noise from 90, 180 and 270 degrees azimuth (S0N3).

The loudspeakers will be located at head height for a seated subject (reference point). The distance from the loudspeaker from the reference point will be approximately one meter. There will be defined locations for the loudspeakers and subject within the test environment.

